## **8.0 RESPONSE ASSESSMENT / SAFETY AND QUALITY ASSURANCE**

### **8.1 Criteria for Response Assessment**

Subjects with measurable disease will be assessed by the RANO (radiographic assessment in neuro-oncology) criteria (Wen 2010). For the purposes of this study, subjects should be re-evaluated at the end of every 2 cycles (approximately every 8 weeks) with a contrast-enhanced cranial MRI scan. The response will be determined as outlined in the RANO criteria below.

*Measurable disease.* Bidimensionally, contrast-enhancing, measurable lesions with clearly defined margins by MRI scan, with a minimal diameter of 1 cm, and visible on 2 axial slices which are at least 5 mm apart with 0 mm skip. Measurement of tumor around a cyst or surgical cavity, if necessary, requires a minimum thickness of 3 mm. If there are too many measurable lesions to measure at each evaluation, the investigator must choose the largest two to be followed before a participant is entered on study. The remaining lesions will be considered non-measurable for the purpose of objective response determination. Unless progression is observed, objective response can only be determined when all measurable and non-measurable lesions are assessed.

Complete Response (requires all of the following):

- a) Complete disappearance of all enhancing measurable and non-measurable disease sustained for at least 4 weeks. In the absence of a confirming scan 4 weeks later, this scan will be considered only stable disease.
- b) No new lesions.
- c) All measurable and non-measurable lesions must be assessed using the same techniques as baseline.
- d) Subjects must be off corticosteroids (or on physiologic replacement doses only).
- e) Stable or improved non-enhancing (T2/FLAIR) lesions.
- f) Stable or improved clinically.

**Note:** Subjects with non-measurable disease cannot have a complete response. The best response possible is stable disease.

Partial Response (requires all of the following):

- a) Greater than or equal to 50% decrease compared to baseline in the sum of products of perpendicular diameters of all measurable enhancing lesions sustained for at least 4 weeks. In the absence of a confirming scan 4 weeks later, this scan will be considered only stable disease.
- b) No progression of non-measurable disease.
- c) No new lesions.
- d) All measurable and non-measurable lesions must be assessed using the same techniques as baseline.
- e) The corticosteroid dose at the time of the scan evaluation should be no greater than the dose at time of baseline scan.
- f) Stable or improved non-enhancing (T2/FLAIR) lesions on same or lower dose of corticosteroids compared to baseline scan.
- g) Stable or improved clinically.

**Note:** Subjects with non-measurable disease cannot have a partial response. The best response possible is stable disease.

Stable Disease (requires all of the following):

- a) Does not qualify for CR, PR, or progression.
- b) The designation of stable disease requires a minimum of 4-week duration.
- c) All measurable and non-measurable sites must be assessed using the same techniques as baseline.
- d) Stable non-enhancing (T2/FLAIR) lesions on same or lower dose of corticosteroids compared to baseline scan. In the event that the corticosteroid dose was increased for new symptoms and signs without confirmation of disease progression on neuroimaging, and subsequent follow-up imaging shows that this increase in corticosteroids was required because of disease progression, the last scan considered to show stable disease will be the scan obtained when the corticosteroid dose was equivalent to the baseline dose.
- e) Stable clinically.

Progressive Disease (defined by any of the following):

- a)  $\geq 25\%$  increase in sum of the products of perpendicular diameters of enhancing lesions compared to the smallest tumor measurement obtained either at baseline (if no decrease) or best response, on stable or increasing doses of corticosteroids.\*
- b) Significant increase in T2/FLAIR non-enhancing lesion on stable or increasing doses of corticosteroids compared to baseline scan or best response following initiation of

therapy,\* not due to co-morbid events (radiation therapy, demyelination, ischemic injury, infection, seizures, postoperative changes, or other treatment effects).

- c) Any new lesion.
- d) Clear clinical deterioration not attributable to other causes apart from the tumor (e.g., seizures, medication adverse effects, complications of therapy, cerebrovascular events, infection, etc.) or changes in corticosteroid dose. The definition of clinical deterioration is left to the discretion of the treating physician, but it is recommended that a decrease in 20% of KPS or from any baseline to 50% or less be considered, unless attributable to comorbid events.
- e) Failure to return for evaluation due to death or deteriorating condition.
- f) Clear progression of non-measurable disease.

\* Stable doses of corticosteroids include patients not on corticosteroids.

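### The notes under complete and partial response in Section 8.1 omit the word 'only', so read literally they bar responders whom the criteria above them accept

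*Combined protocol and SAP*

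**What the plan says.** Objective response (CR plus PR) is the primary endpoint in both arms (Sections 1.0 and 11.0), and Section 8.1 defines it. Four elements of that section bear on this point.

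- **The notes.** Under complete response: "Subjects with non-measurable disease cannot have a complete response. The best response possible is stable disease". Under partial response: "Subjects with non-measurable disease cannot have a partial response. The best response possible is stable disease".
- **The lettered criteria.** CR (a) requires "Complete disappearance of all enhancing measurable and non-measurable disease sustained for at least 4 weeks". PR (b) requires "No progression of non-measurable disease".
- **The assessment rule.** Unless there is progression, "objective response can only be determined when all measurable and non-measurable lesions are assessed".
- **How a lesion becomes non-measurable.** A measurable lesion is one "with a minimal diameter of 1 cm, and visible on 2 axial slices which are at least 5 mm apart with 0 mm skip", so a smaller enhancing lesion does not qualify. There is also a conditional route: "If there are too many measurable lesions to measure at each evaluation, the investigator must choose the largest two to be followed". For the lesions not chosen, "The remaining lesions will be considered non-measurable for the purpose of objective response determination".

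Eligibility item 3 in Section 3.2 requires measurable disease of Arm 1 patients only. It does not exclude further, non-measurable lesions, and it sets no such requirement for Arm 2.

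**The concern.** The lettered criteria take for granted that a responder may have non-measurable lesions: they must vanish for a CR and must not progress for a PR. The notes, taken at their word, say that such a subject cannot respond at all. Two sites could then score the same scans differently, one as PR and the other as stable disease, and each could point to Section 8.1.

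The other safeguards in the plan do not clearly repair this. Sections 8.2 and 8.4 send the scans of subjects showing response to the central neuroradiologist, and a patient whom the site has called stable does not enter by that route. Under Section 8.2 the extra MRI before the next cycle is also triggered by a CR or PR. A site applying the note would not order it, and Section 8.1 counts an unconfirmed response as stable disease. The response could then be confirmed later only if the next scheduled scan, about 8 weeks on, still showed it.

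The stakes are the decision rules in Section 11.0. Each arm needs at least 7 responses, Arm 1 stops at 2 or fewer of 19, and Arm 2 opens only if Arm 1 succeeds.

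**Working it through.** **Step 1: the text.** Take a subject with one measurable lesion and one enhancing lesion under 1 cm. The measurable lesion's product of diameters falls by 70% for 8 weeks and the small lesion does not grow. Steroids, T2/FLAIR and clinical state are all acceptable.

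| Provision | Result for this subject |
|---|---|
| PR (a): fall of at least 50%, held at least 4 weeks | met |
| PR (b): non-measurable disease has not progressed | met |
| PR (c) to (g) | met by construction |
| Lettered criteria together | PR |
| Note under PR, read literally | stable disease |

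On the literal reading, PR (b) and the non-measurable part of CR (a) apply to nobody, because any subject to whom they could apply is already barred. No other section limits the notes.

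**Step 2: reproduce the design figures.** Inputs from Section 11.0:

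- Arm 1: stop at 2 or fewer of 19; success at 7 or more of 31; rates 13% and 30%.
- Arm 2: stop at 2 or fewer of 18; success at 7 or more of 35; rates 10% and 30%.

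Formula, with n1 the stage 1 size, n the total size and p the response rate:

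P(success) = Σ over x from 3 to n1 of Bin(x; n1, p) × P(Y ≥ 7 − x), where Y ~ Bin(n − n1, p)

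P(early stop) = P(X ≤ 2), where X ~ Bin(n1, p)

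| | Power at 30% | Success under null | Early stop under null | Stated in the plan |
|---|---|---|---|---|
| Arm 1 | 0.854 | 0.095 | 0.543 | at least 0.85; at least 0.90 negative; at least 0.54 |
| Arm 2 | 0.902 | 0.047 | 0.734 | at least 0.90; 0.05; 73% |

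All stated figures reproduce. The design arithmetic is not in dispute.

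**Step 3: effect of the notes if applied literally.** Let f be the share of true responders who also have non-measurable lesions and are therefore scored stable. The scored response rate is p(1 − f). The documents give no value for f, so the range below is an assumption. If f is instead thought of as a share of all patients, the same formula also requires that response be unrelated to having non-measurable lesions.

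| f | Scored rate when the true rate is 30% | Arm 1 power | Arm 2 power |
|---|---|---|---|
| 0 (sites infer 'only') | 0.30 × 1.00 = 0.300 | 0.854 | 0.902 |
| 5% | 0.30 × 0.95 = 0.285 | 0.810 | 0.869 |
| 10% | 0.30 × 0.90 = 0.270 | 0.758 | 0.828 |
| 20% | 0.30 × 0.80 = 0.240 | 0.627 | 0.718 |

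At a true rate of 30%, the chance that Arm 1 stops at stage 1 rises from 4.6% at f = 0 to 8.0% at f = 10% and 13.1% at f = 20%.

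**The case against.** The strongest reply is that nobody would read the notes literally. Section 8.1 opens by applying the criteria to subjects with measurable disease, so the subjects named in the notes are naturally the other class, those without any. That reading leaves every neighbouring provision with work to do, and it gives the notes a purpose, since Arm 2 may enrol patients with no measurable lesion. This is persuasive as to intent. It is not what the text says, and in a multicenter trial it relies on every site making the same silent correction to a primary endpoint rule.

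Two stronger readings are tempting, and the documents support neither.

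- *Any third lesion triggers the bar.* Lesions are relabelled only when there are too many to measure at each evaluation. Nothing shows that three are too many. If all three are measured, PR (a) counts all of them and the note is never reached. The case of a lesion under 1 cm does not depend on this condition.
- *The notes do turn responders into stable disease, at a known cost in power.* The documents show neither how sites will read the notes nor how many patients have both kinds of lesion. If only some sites read the notes literally, the loss is smaller than shown for a given f. If none does, it is zero.

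It is also fair to say that any fixed cut-off can turn on one patient. That fact shows what a misread note could cost, but not how likely a misreading is.

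**Conclusion.** The notes are wrong as written: they contradict CR (a), PR (b) and the assessment rule in the same section, and nothing elsewhere limits them. This is a drafting fault in the definition of the primary endpoint. It does not show that the design or its operating characteristics are faulty.

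The patients exposed are those with a measurable lesion plus a sub-centimetre one, and those with lesions left out of the two followed because there were too many to measure. The effect on power runs from none to the f = 20% row of the table. The lower figures assume literal application to every affected patient and a value of f that the documents do not give, so they are scenarios and not expected losses. The contradiction itself is certain; the harm depends on how sites read it. Because response decides both arms and whether Arm 2 opens, and the correction is trivial, it should be made.

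**What to change.** In both notes, replace the opening words with: *Subjects with only non-measurable disease (no lesion meeting the measurable definition at baseline)*. Then add one sentence saying that non-measurable lesions present alongside measurable ones, including measurable lesions not selected for follow-up, are judged under CR (a) and PR (b).

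This keeps the probable purpose of the notes, which is to say how a subject with no measurable lesion is scored, and it leaves the design figures in Section 11.0 as they stand. The cost is a few words in Section 8.1, with no added scans, data or patients.

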## **8.2 Assessment of Response**

Assessment of response will begin with the MRI performed just prior to *every odd-numbered* treatment cycle. If during any scheduled MRI, the subject has a Complete Response or Partial Response, the MRI should be repeated prior to the next cycle. All scans are to be compared to the smallest measurement scan to date. The subject will then return to the every odd-numbered cycle schedule. This is required to confirm the duration of response. Subjects will be classified as responders if they have a minimum duration of response for 4 weeks at any time after the first cycle of TRC102. MRI scans of subjects showing tumor response will be centrally reviewed by a neuroradiologist who will independently assess tumor size and compute percent tumor regression.

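### Section 8.2 names a reference scan that does not match 8.1's definition of partial response, and its confirmatory MRI is missing from the visit schedule

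*Combined protocol and SAP*

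**What the plan says.** **Reference scan.** Section 8.2 states "All scans are to be compared to the smallest measurement scan to date". Section 8.1, Partial Response item a, requires "Greater than or equal to 50% decrease compared to baseline in the sum of products of perpendicular diameters of all measurable enhancing lesions". Section 8.1, Progressive Disease item a, measures growth "compared to the smallest tumor measurement obtained either at baseline (if no decrease) or best response".

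**Confirmation.** Section 8.2 states "If during any scheduled MRI, the subject has a Complete Response or Partial Response, the MRI should be repeated prior to the next cycle", then "The subject will then return to the every odd-numbered cycle schedule". It also states "Subjects will be classified as responders if they have a minimum duration of response for 4 weeks at any time after the first cycle". For both CR and PR, item a of 8.1 adds: "In the absence of a confirming scan 4 weeks later, this scan will be considered only stable disease".

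**Schedule.** The opening of 8.1 says "subjects should be re-evaluated at the end of every 2 cycles (approximately every 8 weeks) with a contrast-enhanced cranial MRI scan". Section 4.1 places MRI before each odd-numbered cycle. The MRI row of Table 9.1 has entries at baseline, pre-odd cycles and off treatment. Its pre-even cell is empty, and none of the 13 footnotes mentions a confirmatory scan. The glucocorticoid-dose row has the same pattern.

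**Steroids.** CR item d and PR items e and f in 8.1 make response depend on the corticosteroid dose when the scan is evaluated.

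**The concern.** Objective response (CR+PR) drives every decision in Section 11: at least 3 of 19 to continue and 7 of 31 to succeed in Arm 1, and at least 3 of 18 and 7 of 35 in Arm 2. Arm 2 opens only if Arm 1 succeeds. With counts this small, the rule that decides whether one patient is a confirmed responder should read the same wherever a site finds it.

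It does not, in two ways. First, 8.2 places a blanket comparison with the smallest scan directly after the confirmation rule, while the 50% threshold in 8.1 is set against baseline. Second, the scan that confirms a response is required in 8.2 but absent from the places where sites look up their visits. Section 12.0 points sites to Section 9.1 for evaluation time points. A site working from the table alone would not do the scan, and 8.1 attaches a penalty to its absence.

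**Working it through.** **1. The plan's own design figures.** For each arm, P(positive | p) is the sum, over first-stage counts x of 3 or more, of P(X₁ = x) × P(X₂ ≥ 7 − x). Here X₁ ~ Bin(n₁, p) and X₂ ~ Bin(n − n₁, p).

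| | Early stop at null | P(positive) at null | Power at 30% | Plan states |
|---|---|---|---|---|
| Arm 1 (n₁ = 19, n = 31, null 13%) | 0.543 | 0.095 | 0.854 | at least 0.54; negative at least 0.90; at least 85% |
| Arm 2 (n₁ = 18, n = 35, null 10%) | 0.734 | 0.047 | 0.902 | 73%; one-sided 0.05; at least 90% |

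All reproduce. The concern is how a response is ascertained, not the design arithmetic.

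**2. Reference scan.** The series are hypothetical sums of products in mm², in the order baseline, scan 1, scan 2. The PR threshold is −50%.

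| Series | Scan 2 against baseline (8.1) | Scan 2 against smallest earlier scan (8.2, literal) |
|---|---|---|
| 1,000, 450, 450 | (450 − 1,000)/1,000 = −55% | (450 − 450)/450 = 0% |
| 1,000, 700, 450 | (450 − 1,000)/1,000 = −55% | (450 − 700)/700 = −36% |

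In the first series, scan 1 is a PR under either rule, because baseline is the only earlier scan. Scan 2 confirms it under 8.1 and fails under the literal 8.2 sentence. In the second series, scan 2 reaches PR under 8.1 but not under 8.2. CR is defined by disappearance rather than a percentage, so the mismatch affects PR only. For progression the two sections agree.

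**3. Where the confirmatory scan is scheduled.** Scheduled MRIs precede odd cycles, so a repeat before the next cycle falls before an even one. The instruction to return to the odd-cycle schedule confirms this.

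Eight rows of Table 9.1 have a pre-odd entry: glucocorticoid dose, AE, MRI, H&P/neuro, KPS, vital signs, CBC and serum chemistry. Six of these also have a pre-even entry. The two that do not are MRI and glucocorticoid dose, the two needed to confirm a response. Footnotes 4, 9 and 13 show that the table does carry conditional items.

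**4. Next scan from the table alone.** Two 28-day cycles are 56 days. Each pre-odd MRI may fall 0 to 5 days before its cycle (footnote 5), so the gap is 56 − 5 = 51 to 56 + 5 = 61 days with on-time cycles. Section 4.3.2 allows each cycle to start up to 3 days late, which extends the maximum to 61 + 6 = 67 days. Both 8.1 and 8.2 work with 4 weeks. The documents do not say whether a scan at about 8 weeks can confirm a response when the 4-week scan was missed.

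**5. Direction if the scan is skipped.** A response that lasts 4 weeks but is over by 8 would be scored as stable disease, which lowers the count. The opposite can also occur. Take 1,000 at baseline, 480 at the responding scan, 560 at week 4 and 480 at week 8. At week 4 the change from baseline is −44%, so confirmation fails; growth from the smallest scan is 80/480 = +17%, below the 25% progression threshold. If the week-4 scan were skipped and the week-8 scan (−52%) accepted, this patient would count as a confirmed responder.

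**The case against.** The strongest reply is that the rule is already in the protocol. Section 8.2 gives the repeat scan's trigger, timing and purpose, and the CR and PR definitions in 8.1 call for it again. A site has to use those definitions to declare a response, so it meets the requirement when it applies. Nor is Table 9.1 exhaustive: it omits the repeat imaging recommended in 4.4 for suspected clinical deterioration and the survival follow-up in 10.2. This stands. The schedule point is an omission. A reader might infer that the documents contradict each other on whether confirmation is required, and they do not.

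On the reference scan, 8.1 ties PR expressly to baseline. The literal 8.2 reading would make confirmation of PR almost impossible, so a careful reader would reject it. That lowers the risk but does not remove it, because 8.2 says all scans and makes no exception for response. Central review (8.2 and 8.4) helps only in part: it covers patients already showing response, names no reference scan, and cannot supply an MRI that was not done.

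Three stronger readings are tempting and not supported:

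- A reader might infer that errors here can only reduce the response count. Step 5 gives a counterexample.
- A reader might infer that, under the literal 8.2 rule, a gradual responder could never be called PR. If the second series in step 2 went on to 220 mm², the change would be (220 − 450)/450 = −51% even against the smallest scan.
- A reader might infer a definite loss of power, or a bound on it. The documents give neither a response duration nor a rate at which the scan would be missed, so any such figure would rest on invented inputs.

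**Conclusion.** The point holds in two parts. The 8.2 reference-scan sentence is wrong as written for PR: applied literally, it turns a sustained 55% reduction into no confirmed response. The absence of the confirmatory MRI and its steroid-dose record from Table 9.1, and of the scan from 4.1 and the opening of 8.1, is a smaller matter that does harm only where 8.2 is overlooked.

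The size of either effect cannot be derived from the documents. For a skipped scan even the direction is open, because it depends on whether an 8-week scan may confirm. No figure in Section 11 needs to change. I would rate this between a minor correction and one that should be made: the chance of error is modest, but the endpoint is primary, the decision counts are small and the correction is cheap. The mm² series are illustrations, and the scan intervals assume no toxicity delay.

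**What to change.** 1. In 8.2, replace the reference-scan sentence with: 'Response is judged against the baseline scan; progression is judged against the smallest measurement to date.'
2. In Table 9.1, add MRI and glucocorticoid dose to the pre-even column, with the footnote 'required when the preceding scheduled MRI showed CR or PR'.
3. Cross-reference that exception in the MRI sentence of 4.1 and in the opening of 8.1.

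Two optional details could be settled in the same edit. The new MRI cell should not take footnote 5 unmodified, because its window would allow scans 28 − 5 = 23 days apart against the 4-week minimum. The team could also state whether a response still present at the next odd-cycle MRI counts as confirmed when the pre-even scan was missed.

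The cost is one sentence, two conditional cells with a footnote, two short clauses, and one steroid-dose entry per confirmatory scan. No scan is added beyond those 8.2 already requires, and the sample size and decision rules stay as they are.

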## **8.3 Safety assessments**

Safety assessments will consist of monitoring and recording all adverse events and serious adverse events, the regular monitoring of hematology and blood chemistry, regular measurement of vital signs, and the performance of physical/neurological examinations.

## **8.4 Quality Assurance**

**Neuropathology:** The neuropathologic diagnosis of glioblastoma will be made at the respective institution. If any question arises regarding the accuracy of the neuropathologic diagnosis, slides (and pathological blocks, if necessary) will be reviewed by the central review pathologist. For protocols with “response” as an outcome, all patients with a documented complete response or partial response will have representative pathology slides undergo central review.

**Neuroradiology:** MRI scans of patients showing tumor response will be centrally reviewed by a neuroradiologist who will independently assess tumor size and compute percent tumor regression.

**Neuro-oncology:** The local investigator at the participating institution will communicate to the ABTC Central Office any unexpected neurological effects such as change in seizure frequency, alteration in neuromuscular function, alteration in cognitive function, or fluctuations in serum anticonvulsant drug levels.

**Adherence to protocol therapy:** Screening/baseline source documentation will be submitted/uploaded into CTEP's iMedidata Rave system and will be reviewed by the ABTC Central Office. As a quality assurance measure for the treatment delivered on this protocol, primary patient records may be reviewed. The records to be examined will be selected retrospectively and at random; complete records must therefore be maintained on each patient treated on the protocol. These records should include primary documentation (e.g., laboratory report slips, X-ray reports, scan reports, pathology reports, physician notes, etc.), which confirm that:

- The patient met each eligibility criterion.
- Signed informed consent was obtained prior to treatment.
- Treatment was given according to protocol (dated notes about doses given; any reasons for any dose modifications).
- Toxicity was assessed according to protocol (laboratory report slips, etc.).
- Response was assessed according to protocol (MRI scan, lab reports, dated notes on measurements and clinical assessment, as appropriate).
- NCI Drug Accountability Records were maintained for this protocol.

